#### 12C2. Adverse Drug Toxicity for Combination therapy pilot study

An adverse drug toxicity will be defined as any of the following at the 2 or 6 week time point:

- Serious infection qualifying as an SAE (see Section 13) and requiring intervention
- A decrease in the white blood cell count (WBC) to <1500/mm^3 (Grade 3 severity by NIH/NIAID) (NIH 2009)
- An anaphylactoid reaction to an injection of anakinra
- ALT or AST more than 3x the upper limit of age and sex-adjusted normal AND >50% increase over baseline (pre-IVIG)
- CK elevation > 10 times the upper limit of normal or symptoms of muscle pain due to myositis
- A decrease in total cholesterol (TC) level that is at least 10% lower than entry level AND below 100 mg/dl (~2.5th percentile for children age 2 yrs.)

A low absolute neutrophil count (ANC) is considered part of the natural course of KD and usually occurs 2 weeks after the initial illness ([name] 2011). Given this, a low ANC will not be considered an adverse drug toxicity or an adverse event in this study.

#### 12D. Dose Escalation for the Phase I/IIa anakinra study

The first 3 subjects in the study will be treated with 4 mg/kg/day as an IV dose of 2 mg/kg q 12 h and then as 4 mg/kg/day SQ for 2-6 weeks. If there are no dose limiting toxicities after 2-6 weeks of therapy, the safety and clinical data will be tabulated and presented to the PI, co-investigators and the Data Safety Monitoring Board (DSMB) for evaluation as to opening the next dose level (6 mg/kg) (**Tables 5 and 6**). Additional subjects will be enrolled at the highest dose if a dose limiting toxicity is not reached at 8 mg/kg/day for further study in the Phase IIa (total number of subjects is 30).

Table 6. Dose Escalation Decision Rules				
Subjects with a	Escalation Decision Rule			
DLT at a Given Dose				
0 out of 3	Enter 3 patients at the next dose level until maximum tolerated dose.			
1 out of 3	Enter a total of 6 patients at this dose level.			
	• If 0 of these additional patients experience a DLT, proceed to the			
	next dose level.			
	
 
If 1 of these additional patients experiences a DLT, then dose
 
			
	escalation is stopped (see below)			
≥ 2	At least 3 additional patients will be entered at the next lowest dose			
	level if only 3 patients were treated previously at that dose. This lower			
	dose level will be declared the MTD.			

Probability of Dose Escalation: The following probabilities of dose escalation (**Table 7**) are computed as the sum of the binomial probabilities of the following two possible outcomes that would allow dose escalation to occur: (1) no DLT observed in the first three subjects; or (2) one DLT observed in the first three subjects, followed by no DLT observed in three additional subjects at the same dose level. For example, when the underlying DLT rate is no more than 15%, the probability of dose escalation will be at least 81% or alternatively 19% probability of early study termination. Exact 95% binomial confidence intervals will be used to describe the rate of successful dose escalation.

Table 7: The probabilities for dose escalation in Phase I					
True but unknown DLT rate ≤0.1 ≤0.15 ≤0.2 ≤0.3 ≤0.4					
Probability of escalation	≥91%	≥81%	≥71%	≥49%	≥31%

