### 11B. Inclusion

#### 11B1. Inclusion for Phase I/IIa anakinra study

- Meets clinical criteria for KD according to American Heart Association guidelines (Table 4): Fever (T≥38°C or 100.4°C) ≥ 3 days and ≥ 2 clinical criteria with LAD or RCA z-score ≥ 2.5
- 2. Patient is at least 28 days old
- 3. Patient presents within the first 20 days after fever onset
- 4. Parent or legal guardian able and willing to provide informed consent
- 5. Able to be dosed between 20 mg (min amount on syringe) and 200 mg at 8 mg/kg/day

Dose escalation level*	Minimum subject weight to administer 20 mg	Maximum subject weight to administer 200 mg
8 mg/kg	2.5 kg	25 kg

\*This table includes only the 8 mg/kg dose level as enrollment in the 4 and 6 mg/kg cohorts has been completed as of the Nov 2016 revision.

\*As of the August 2017 revision, we have enrolled 2 subjects at 8mg/kg/day without any dose limiting toxicities.

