### 12E. Maximum Tolerated Dose for Phase I/IIa anakinra study

The Maximum Tolerated Dose (MTD) will be defined as the highest dose of anakinra studied at which no more than one in six patients experiences a DLT during the 6 weeks of treatment. Subjects will be enrolled at the maximum tolerated dose until a total of 30 subjects have been enrolled in the study. Given the 3+3 design of the study, if there is a DLT then a total of 6 subjects will enrolled per dose level. If we reach the 8 mg/kg/day dose level, then up to a maximum of 12 subjects will be enrolled at a dose level below the MTD (4 mg/kg and 6 mg/kg). This leaves 18 subjects treated at the MTD if the third dosing level is reached. If there are no DLTs at the first two levels, then 3 subjects will be enrolled at the MTD. Thus, between 18 and 24 subjects will be enrolled at the MTD if the 3rd dose level is reached.

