### 12F. Stopping Rules

#### 12F1. Stopping rules for Phase I/IIa anakinra study

**Individual stopping rule:** A subject who experiences a DLT will discontinue anakinra immediately and will be monitored for resolution of the toxicity as medically appropriate. All subjects will be monitored for the 6 weeks from the time of enrollment or until resolution of the DLT, whichever is later.

**Study stopping rule:** Table 6 shows the Phase I dose escalation rules. The study will be discontinued if at the first dose (4 mg/kg/day), the number of subjects that experiences a DLT is greater than 2. Otherwise, the study will determine its MTD using the escalation rules described.

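### Table 6 declares the next lower dose the MTD whatever happens to its added patients, so a level ending at 2/6 or 3/6 DLTs is the MTD there but is excluded by Section 12E

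*Combined protocol and SAP*

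**What the plan says.** Three sections of the combined protocol and SAP bear on how the MTD is set.

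- **Section 12D, Table 6.** A level with no DLT in 3 leads upward: "Enter 3 patients at the next dose level until maximum tolerated dose". When two or more subjects at a level have a DLT, the plan goes down: "At least 3 additional patients will be entered at the next lowest dose", provided that only 3 were treated there before. The row closes by saying that this lower "dose level will be declared the MTD". It sets no requirement on what the added patients show.
- **Section 12E.** The MTD is the highest dose studied at which "no more than one in six patients experiences a DLT during the 6 weeks of treatment". Enrolment then continues at the MTD until the study has 30 subjects.
- **Section 12F1.** The study stops if, at 4 mg/kg/day, "the number of subjects that experiences a DLT is greater than 2". It goes on: "Otherwise, the study will determine its MTD using the escalation rules described".

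On the state of the trial, Section 11B1 reports as of August 2017 that "we have enrolled 2 subjects at 8mg/kg/day without any dose limiting toxicities". It also says that the 4 and 6 mg/kg cohorts are complete, without giving their sizes. Section 1 says that 8 mg/kg/day was still accruing in September 2017.

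**The concern.** Patients are added at the lower level to find out whether that dose is tolerable with six treated. As Table 6 is worded, their results cannot change the decision. A level with only 3 patients must have been 0/3 to allow escalation, so 3 more can bring it to anything from 0/6 to 3/6. At 2/6 or 3/6, Table 6 calls it the MTD and Section 12E says that it is not.

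The label has consequences, because it fixes the dose for everyone enrolled afterwards up to 30. The rule comes into use only after toxicity has appeared in children at the higher dose, which is when the investigators most need a single clear instruction.

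There is a related gap at the lowest dose. Section 12F1 stops the study at 4 mg/kg/day only with more than 2 DLTs. A result of 2/6 there neither stops the study nor meets Section 12E, and there is no lower level to move to.

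**Working it through.** **Inputs from the plan.** The escalation and de-escalation rules are in Table 6, the limit of one in six and the total of 30 in Section 12E, and the cohort sizes of 3 to 6 in Table 5. The plan gives no expected DLT rates for any dose. The rates below are assumptions, shown over a range.

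**1. Reproduce Table 7.** Escalation needs 0/3, or 1/3 followed by 0/3:

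esc(p) = (1−p)³ + 3p(1−p)²·(1−p)³ = (1−p)³ + 3p(1−p)⁵

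| True DLT rate | 0.10 | 0.15 | 0.20 | 0.30 | 0.40 |
|---|---|---|---|---|---|
| Computed | 90.6% | 81.4% | 70.9% | 49.4% | 30.9% |
| Table 7 | 91% | 81% | 71% | 49% | 31% |

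Table 7 is reproduced. It covers escalation only and says nothing about the de-escalation step.

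**2. Chance that the added patients break the 12E limit.** The lower level starts at 0/3, so its final count is X ~ Bin(3, p) among the 3 added:

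P(X ≥ 2) = 3p²(1−p) + p³

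| True rate at lower dose | P(2/6) | P(3/6) | P(2/6 or 3/6) |
|---|---|---|---|
| 0.10 | 0.027 | 0.001 | 0.028 |
| 0.20 | 0.096 | 0.008 | 0.104 |
| 0.30 | 0.189 | 0.027 | 0.216 |
| 0.40 | 0.288 | 0.064 | 0.352 |

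**3. Chance of the whole branch, from the start of the lower level.** It needs 0/3 at the lower dose, no escalation beyond the higher dose, and 2 or more DLTs in the 3 added. With pL and pH the lower and higher DLT rates:

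(1−pL)³ × [1 − esc(pH)] × P(X ≥ 2 | pL)

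- 0.10/0.30: 0.729 × 0.506 × 0.028 = 0.010
- 0.20/0.40: 0.512 × 0.691 × 0.104 = 0.037
- 0.30/0.50: 0.343 × 0.828 × 0.216 = 0.061

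**4. Chance of the branch from where the trial stood.** Assume that 6 mg/kg closed at 0/3 and that the two 8 mg/kg subjects are evaluable and DLT-free. The third 8 mg/kg patient must then have a DLT, followed by at least one DLT in the next three:

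pH·[1 − (1−pH)³] × P(X ≥ 2 | pL)

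- 0.10/0.30: 0.197 × 0.028 = 0.0055
- 0.20/0.40: 0.314 × 0.104 = 0.033
- 0.30/0.50: 0.438 × 0.216 = 0.095

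**5. Children enrolled afterwards if Table 6 is followed.** With 6 treated at 6 mg/kg and 6 at 8 mg/kg:

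- 3 treated at 4 mg/kg: 30 − 3 − 6 − 6 = 15
- 6 treated at 4 mg/kg: 30 − 6 − 6 − 6 = 12

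If 8 mg/kg closes as soon as a second DLT occurs in its fourth patient, the counts become 30 − 3 − 6 − 4 = 17 and 30 − 6 − 6 − 4 = 14.

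**The case against.** The best reply is that the protocol, read sensibly, already resolves this.

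- **Re-apply the row.** The Table 6 row for two or more DLTs has no denominator and is not limited to the ascending phase. A lower level ending at 2/6 or 3/6 falls under it again, which sends enrolment down another level. That is a reasonable way to run a sequential rule, but it contradicts the row's own unconditional declaration and gives no answer at 4 mg/kg/day.
- **Let Section 12E govern.** The instruction to enrol up to 30 sits directly after the definition, so the dose meant there is naturally one that meets the definition. Adding patients to reach six also makes little sense unless the limit then applies. This is a fair reading, and it means that the extra exposure arises only if Table 6 is followed over 12E. No text says that 12E prevails, however, and Section 12F1 refers the MTD decision to the escalation rules.
- **Oversight.** The data and safety monitoring board (DSMB) evaluates the opening of each next dose level (12D) and is to set stopping rules (20A), and there are monthly safety calls. These might catch the problem, but the documents contain no rule for this case.
- **Section 12F1 already stops 3/6 at 4 mg/kg/day.** That is correct. It leaves 2/6 open there and does nothing at 6 mg/kg/day.
- **The branch is remote.** This stands in large part. It needs 2 or more DLTs at 8 mg/kg after two DLT-free subjects, exactly 3 patients treated at 6 mg/kg, and 2 or more DLTs in the 3 added. Section 1 reports no drug-related serious adverse events so far, which favours the low end of the assumed rates.

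**Conclusion.** The two rules conflict as written. A level that goes from 0/3 to 2/6 or 3/6 is the MTD under Table 6 and is excluded by Section 12E, and no text ranks one above the other.

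The event is uncommon: about 1% to 6% from the start of the lower level for the assumed pairs of rates, or 0.6% to 9.5% given the position at this version. Those figures rest on assumed DLT rates. The second range also rests on a 6 mg/kg cohort of exactly 3 with no DLT, which the documents do not state. The consequence would be 12 to 17 further children treated at a dose over the protocol's own limit, if Table 6 were the rule applied.

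The primary safety outcome is reported descriptively and does not change. Because the 8 mg/kg cohort was still open, the rule should be corrected on safety grounds despite the low probability.

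**What to change.** In Table 6, replace the unconditional declaration with wording such as: *The lower level becomes the MTD only if no more than 1 of its 6 patients has had a DLT. Otherwise the same rule is applied to the level below it or, at 4 mg/kg/day, enrolment stops and no MTD is named.*

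In Section 12F1, change the threshold at 4 mg/kg/day from more than 2 DLTs to 2 or more, so that it uses the same limit as 12E and closes the 2/6 gap.

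The cost is one sentence and one phrase in a protocol amendment. No subjects or visits are added, and Table 7 stays as it is because it describes escalation only.

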# **12. Dosing Protocol**

#### 12A. Dose Levels

#### 12A1. Dosing for Phase I/IIa anakinra study

All subjects will be treated with IVIG (2g/kg) and aspirin (30-50 mg/kg/day divided every 6 hours; lowered to 3-5 mg/kg/day once sent home), which is the standard of care. In order to minimize the pain from subcutaneous injections, the first two doses of anakinra have been administered intravenously and divided every 12 hours for the dose escalation part of the study (i.e. 4 mg/kg/day is 2 mg/kg every 12 hours for two doses). As has been published in the peer-reviewed literature, we administered the dose by bolus over a 1 to 3 minute period (Opal 1997). As anakinra is formulated for intravenous administration, dilution is not necessary prior to administration. The unused material is discarded in a medical waste container after each administration. See **Appendix A** for details regarding preparation of the study drug for administration of less than 20 mg.

All subsequent doses are administered subcutaneously starting 24 hours after the first dose of the medication. This study has 3 dose levels (4 mg/kg/day, 6 mg/kg/day, and 8 mg/kg/day), with a maximum dosage of 200 mg daily (**Table 5**).

If the daily dose of anakinra for a subject is  $\leq$  100mg, then the subject will receive a subcutaneous injection of anakinra once daily. If the daily dose of anakinra is greater than 100 mg (with a max dose of 200 mg daily), then the dose will be split in half with administration subcutaneously every 12 hours (i.e. a total daily dose of 150 mg will be administered as 75 mg subcutaneously every 12 hours).

Table 5. Dose Levels					
Dose Cohort	Dose Level	Number of Subjects			
1	4 mg/kg/day	3-6			
2	6 mg/kg/day	3-6			
3	8 mg/kg/day	3-6			
ТОТ	AL	9-18			

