# **19. Statistical Analyses**

# 19A. Statistical analysis of safety for Phase I/IIa anakinra study and Combination therapy pilot study

Descriptive statistics will be calculated for demographic and baseline characteristics, variables related to biologic activity, immunologic variables, PK variables, and safety data. The study population will be described using summary descriptive statistics such as mean, median, standard deviation, and range for continuous variables and frequencies for categorical variables. All events (AEs, SAEs, and UPRs) will be recorded, documenting the course, outcome, severity, and

relationship to the study treatment. Incidence rates of events and the proportion of subjects prematurely withdrawn from the study due to events will be compiled. Analyses will be performed for all patients who have received at least one dose of study treatment. Deviation from the treatment plan will be recorded in the case report forms. The percentage of subjects failing to complete the study or discontinuing prematurely (as well as the times and reasons for discontinuation) will be reported. Refer to Section 12E for the operating characteristics of the Phase I dose escalation for the Phase I/IIa anakinra study.

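### Section 12D labels as early study termination a 19% figure that is the chance of not escalating at one dose level

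*Combined protocol and SAP*

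**What the plan says.** Section 12D defines escalation as either of two outcomes: "no DLT observed in the first three subjects", or "one DLT observed in the first three subjects, followed by no DLT observed in three additional subjects at the same dose level". Table 7 tabulates the resulting probability for true DLT rates of 10, 15, 20, 30 and 40%. The text interprets one column. For a rate of at most 15% it says that "the probability of dose escalation will be at least 81% or alternatively 19% probability of early study termination".

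Four other places bear on what happens when escalation fails:

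- **Table 6 (12D).** One DLT in the first three and one more in the next three stops escalation. Two or more DLTs send the study to the next lower level, which becomes the MTD.
- **Section 12E.** The MTD is the highest dose with no more than one DLT in six patients, and enrolment continues at the MTD to 30 subjects in all.
- **Section 12F1.** The study is discontinued if, at 4 mg/kg/day, "the number of subjects that experiences a DLT is greater than 2". In every other case it goes on to find the MTD.
- **Section 19A.** For the "operating characteristics of the Phase I dose escalation" it sends the reader to Section 12E, although they appear in 12D.

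**The concern.** The 81% is the chance of passing a single dose level, so its complement is the chance of not passing that level. The sentence presents the complement as the chance that the study ends early. Under the plan's own rules these are different events.

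This is the only operating characteristic that the plan puts into words, and 19A refers back to the operating characteristics, though under the wrong section number. A report that repeated the sentence would credit the design with a termination property that it does not have. The wording also hides a gap: the plan does not say what happens after exactly two DLTs at the lowest dose.

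**Working it through.** **Inputs.** The DLT rate is p = 0.15, the upper limit in the 12D example. The escalation outcomes are from 12D, the cohort rules from Table 6 and the stopping threshold from 12F1. Cohorts are taken as independent.

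**1. Reproduce the plan's figure (one level).**

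- P(0 of 3) = 0.85³ = 0.6141
- P(1 of 3) = 3 × 0.15 × 0.85² = 0.3251
- P(escalate) = 0.6141 + 0.3251 × 0.6141 = 0.8138
- P(not escalate) = 1 − 0.8138 = 0.1862

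These are the stated 81% and 19%. The same formula gives 0.906, 0.814, 0.709, 0.494 and 0.309 across Table 7, which agrees with the printed row to rounding.

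**2. Probability of meeting 12F1 (three or more DLTs at 4 mg/kg).** Table 6 adds subjects at the same level only after 1 of 3, so the path is 3 of 3, or 1 of 3 followed by at least 2 of 3.

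- P(3 of 3) = 0.15³ = 0.0034
- P(at least 2 of 3) = 3 × 0.15² × 0.85 + 0.0034 = 0.0608
- P(12F1 met) = 0.0034 + 0.3251 × 0.0608 = 0.0231

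The result depends on how 12F1 is read:

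| Reading of 12F1 | Probability at a 15% rate |
|---|---|
| 3 of 3 only | 0.3% |
| Counted along the 3+3 path | 2.3% |
| A cohort with 2 of 3 is still filled to six: 0.0231 + 0.0574 × (1 − 0.6141) | 4.5% |
| DLTs during expansion at 4 mg/kg, to 30 subjects in all, also count | about 13 to 15% |

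The last row adds 10.5% to the second or third row. That is the chance that the study falls back from 6 to 4 mg/kg and then accumulates more than two DLTs there, with 15% at both doses.

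**3. Where 19% could come from as a termination probability.** Two or more DLTs at 4 mg/kg along the 3+3 path is the same event as not escalating from 4 mg/kg, with probability 0.1862. It splits as follows:

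- Exactly two: P(2 of 3) + P(1 of 3) × P(1 of 3) = 0.0574 + 0.3251² = 0.1631
- Three or more: 0.0231

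Most of the 19% is therefore exactly two DLTs, an outcome that does not meet the 12F1 threshold.

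**4. Reaching 8 mg/kg (for information).** Two levels must be passed. With 15% at both, 0.8138² = 0.6623 reach 8 mg/kg and 0.3377 do not: 0.1862 stop at 4 mg/kg and 0.8138 × 0.1862 = 0.1515 stop at 6 mg/kg. With 15% at 6 mg/kg and 0, 5 or 10% at 4 mg/kg, the chance of not reaching 8 mg/kg is 19, 21 or 26%.

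**The case against.** The strongest defence is that the sentence describes failure at the starting dose. There is no level below 4 mg/kg for Table 6 to fall back on, and two or more DLTs there cannot satisfy the 12E definition of the MTD. No studied dose would then qualify, and the study might in effect end. That event has a probability of 18.6%, the stated 19%.

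This stands in part. It shows that failure to escalate cannot be said always to lead to an MTD: it does so above 4 mg/kg, not at 4 mg/kg. It does not rescue the sentence. The calculation is not limited to 4 mg/kg, and 12F1 sets the threshold at more than two DLTs. What it exposes is a disagreement between sections, and the documents do not show which was intended.

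Two further objections are sound. First, a reader might infer that 19% should have been 34%, the chance of not reaching 8 mg/kg. The plan never states a probability of reaching 8 mg/kg, so 34% corrects nothing in it. It is also an upper bound that needs a 15% rate at both 4 and 6 mg/kg. Second, a reader might infer that termination has a fixed probability of a few percent at most. That depends on the reading of 12F1. Its link to the Phase I rules of Table 6 supports counting only the escalation subjects, but it does not expressly exclude expansion subjects.

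**Conclusion.** The 81% and 19% are arithmetically correct for one dose level at a 15% DLT rate, and Table 7 stands. The description of the 19% as early study termination is wrong as written. The only numerical study-level stopping rule for this part, 12F1, has a probability of about 2.3% at that rate along the 3+3 path. No reading of it examined here gives 19%. Section 20A leaves further stopping rules to the DSMB and the investigators, but gives no figures for them.

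The 19% equals a termination probability only if any two or more DLTs at 4 mg/kg ended the study, which contradicts 12F1. Exactly two DLTs at that dose (16.3%) leaves Table 6 without a workable action and no dose that meets 12E. These results assume a common 15% rate and independent cohorts.

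The practical weight is low. Section 11B1 records that enrolment at 4 and 6 mg/kg is complete, the Introduction says that 8 mg/kg is accruing, and the 19% enters no sample size or analysis.

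**What to change.** - In 12D, replace the second half of the sentence with: *at most 19% probability of not escalating at a given dose level when the DLT rate at that level is no more than 15%*. Optionally add: *at most 34% probability of not reaching 8 mg/kg if the rate is no more than 15% at both 4 and 6 mg/kg*.
- Remove the reference to early study termination, or give the termination probability with the reading of 12F1 and the subjects counted.
- Reconcile 12D (with Table 6), 12E and 12F1 on the outcome of exactly two DLTs at 4 mg/kg. Which rule applies is for the investigators and the DSMB to state. The probability quoted should then follow from it.
- In 19A, change the cross-reference for the operating characteristics from 12E to 12D.

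The cost is one rewritten sentence, one clarification and one cross-reference, with no new data or analysis.
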